To address questions regarding dosing both in terms of efficacy and safety, we will plan for an “early phase” of the study, which will essentially serve as a nested dose-response study. In this “early phase” we will randomize the first 45 subjects to one of 3 study arms (placebo, midodrine 10 mg thrice daily or midodrine 20 mg thrice daily). For the interim analysis of this “early phase”, a final sample size of 15 patients per group will provide 80% power to detect a 5 mcg/min decrease in norepinephrine equivalents at 24 hours.

Together with our “early phase” nested study and anticipating a 25% mortality in patients with septic shock we would need to enroll 115 patients to reach statistical significance. Enrolling 115 patients would allow randomization of 50 patients to placebo and 50 patients to the midodrine dose continued following the “early phase” (either 10 or 20 mg depending on the results of our interim analysis at which time we will evaluate both the safety and efficacy of both dosing strategies and continue the lowest dose that is both safe and efficacious). The additional 15 subjects would be required for the early dose-response portion of the study.

In brief:

115 total subjects: 50 placebo, 50 midodrine (either 10mg or 20mg); 15 additional subjects for the “early phase” portion of the study

2. Describe expected rate of screen failure/ dropouts/withdrawals from all sites.

Average mortality in septic shock is anticipated to be around 25-30%. Screen failure is anticipated to be around 20%, mostly due to patients with decompensated cirrhosis. This is based on our MICU septic shock database.

3. How many subjects will be enrolled at all sites?

149

4. How many subjects will sign a consent form under this UVa protocol?

149

Inclusion/Exclusion Criteria

1. List the criteria for inclusion

- Patients aged \geq 18-89 years old
- Admitted to UVA medical ICU with diagnosis of septic shock.
- Patients requiring at least 5 mcg/min norepinephrine infusion (or equivalent) for blood pressure support for at least 3 hours
- Patients with enteral access established within 12 hours of admission (either able to swallow, or feeding tube in place)

2. List the criteria for exclusion

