- Midodrine HCl has been used in patients concomitantly treated with salt-retaining steroid therapy (i.e., fludrocortisone acetate), with or without salt supplementation. The potential for supine hypertension exists in these patients and may be minimized by either reducing the dose of fludrocortisone acetate or decreasing the salt intake prior to initiation of treatment with Midodrine HCl.
- Alpha-adrenergic blocking agents, such as prazosin, terazosin, and doxazosin, can antagonize the effects of Midodrine HCl.

Patients will be continuously monitored in ICU and the goal of the study is to raise blood pressure.

Statistical Considerations

1. Is stratification/randomization involved?

YES

► IF YES, describe the stratification/ randomization scheme.

After enrollment, patients will initially be randomized employing a block of 9 randomization scheme generated by the study investigators. Allocation will be performed manually; there will be 5 envelopes, each envelop for a sequence of 9 patients. Each envelope will contain 3 cards for the placebo group and 3 cards for the midodrine 10 mg TID treatment group and 3 cards for the midodrine 20 mg TID treatment group. Cards will be pulled out of the envelope to randomize the patients. Once 9 patients are randomized the next envelop will be opened.

Following interim analysis of the first 45 patients, one of the treatment groups will be dropped with preference given to dropping the midodrine 20 mg TID group should interim analysis demonstrate similar, significant effect sizes in both treatment groups. Additionally, the safety profile of both dosing strategies will be considered prior to continuing the experimental arm of the study.

Subsequently, the remaining 104 patients will be randomized employing a block of 8 randomization scheme generated by the study investigators. Allocation will be performed manually; there will be 13 envelopes, each envelop for a sequence of 8 patients. Each envelope will contain 4 cards for the placebo group and 4 cards for the continuing midodrine group (either 10 mg TID or 20 mg TID). Cards will be pulled out of the envelope

to randomize the patients. Once 8 patients are randomized the next envelop will be opened.

► IF YES, who will generate the randomization scheme?

Sponsor
 UVa Statistician. Answer/Response:
 UVa Investigational Drug Service (IDS)
 Other: Answer/Response: Investigators
UVa Investigational Drug Service (IDS)

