2. What are the statistical considerations for the protocol?

We will compare placebo group versus the midodrine intervention group for all primary analyses and use the Mann-Whitney U test to assess the primary outcome, which is assumed to be non-parametric.

3. Provide a justification for the sample size used in this protocol.

To estimate the sample size, we used the UVA Clinical data repository (CDR) to identify 960 patients who would have met our study enrollment criteria (patients receiving IV vasopressors for >3 hours, with a diagnosis of sepsis, without cirrhosis, and not receiving midodrine). We then extracted their duration of vasopressors and the total norepinephrine equivalent doses at 24 hours. We performed repeated simulation of bootstrapped samples to estimate power from these populations with varying sample and effect sizes. Based on these estimates, we believe that a final sample size of 50 per group will provide 80% power to detect a 12-hour difference in duration of IV vasopressors (our primary end point) based on a 2-arm study design (placebo vs midodrine). These calculations compare favorably with those obtained assuming a normal distribution, based on a mean IV vasopressor duration of 54.9 hours (SD 28.4 h) in patients with septic shock as published in a recent trial⁹, which calculations would require randomization of 49 patients to each group to detect an effect of 18 hours difference in IV vasopressor duration at a power of 80% and an alpha value of 0.05. However, because our calculations are based on internal data (and so should reflect our practices of vasopressor weaning) and because the distribution of IV vasopressor duration is non-normal, we believe that sample size calculation based upon our CDR analysis is more accurate.

To address questions regarding dosing both in terms of efficacy and safety, we will plan for an “early phase” of the study, which will essentially serve as a nested dose-response study. In this “early phase” we will randomize the first 45 subjects to one of 3 study arms (placebo, midodrine 10 mg thrice daily or midodrine 20 mg thrice daily). For the interim analysis of this “early phase”, a final sample size of 15 patients per group will provide 80% power to detect a 5 mcg/min decrease in norepinephrine equivalents at 24 hours.

Together with our “early phase” nested study and anticipating a 25% mortality in patients with septic shock would need to enroll 149 patients to reach statistical significance.

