Secondary outcomes will include ICU and hospital length of stay as well as central venous catheter dwell time. Because IV vasopressor duration cannot be assumed to have a normal distribution, we intend to analyze our primary outcome using the Mann-Whitney U test.

4. What is your plan for primary variable analysis?

Dose of IV vasopressor(s) at 24 hours and hours requiring IV vasopressor therapy will be the primary outcomes of interest for the “early phase” and complete study, respectively. Because IV vasopressor duration and dose cannot be assumed to have normal distributions, we intend to analyze our primary outcome using the Mann-Whitney U test.

5. What is your plan for secondary variable analysis?

1. Central venous catheter free days
2. Hospital length of stay
3. Intravenous Vasopressor free days
4. 28-day mortality
5. ICU mortality
6. Need for re-initiation of vasopressor therapy after discontinuation for >2 hours

We will employ the Chi square test for binary outcomes. Furthermore, we will use regression analyses with appropriate interaction terms.

6. Have you been working with a statistician in designing this protocol?

No

IF YES, what is their name?

Answer/Response:

N/A

7. Will data from multiple sites be combined during analysis?

No

INSTRUCTIONS: IF YES, answer the following questions

7(a). Does the study involve randomization?

Answer/Response:

IF YES, will randomization be done at each site or among sites?

Answer/Response:

7(b). Has the sample size calculation considered the variation among sites?

Answer/Response:

7(c). When combining the data from multiple sites to assess the study results, is the effect of the treatment to be tested (or the association to be tested) assumed to be the same across sites or vary among sites? What is the modelling strategy?

Answer/Response:

7(d). Is there a common protocol used in all sites?

Answer/Response:

IF NO, how will differences among sites, such as those related to the implementation, inclusion criteria, patient characteristics, or other sites characteristics, be considered to assess the study results?

Answer/Response:

Study Procedures-Biomedical Research

1. What will be done in this protocol?

Screening:

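### An optional gain rather than an error: both primary Mann-Whitney tests are valid but unadjusted, although vasopressor dose before randomisation could be a pre-specified covariate

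*Combined protocol and SAP*

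**What the plan says.** The early phase compares vasopressor dose at 24 hours; the complete study compares hours on IV vasopressor (Statistical Considerations, item 4). For both, the plan reasons that "IV vasopressor duration and dose cannot be assumed to have normal distributions, we intend to analyze our primary outcome using the Mann-Whitney U test". Neither item 2 nor item 4 names a covariate. Regression appears once, under the secondary outcomes in item 5: "Furthermore, we will use regression analyses with appropriate interaction terms". No covariate is named there either.

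Randomisation is blocked with no stratification factor (item 1). Early-phase envelopes hold three cards per arm; later, "Each envelope will contain 4 cards for the placebo group and 4 cards for the continuing midodrine group".

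The inclusion criteria admit "Patients requiring at least 5 mcg/min norepinephrine infusion (or equivalent) for blood pressure support for at least 3 hours", with no upper limit. Screening is by review of the medical record, and vasopressor dose is on the list of data to be collected (Study Procedures, item 1).

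On size (Statistical Considerations, item 3), the plan states that "a final sample size of 50 per group will provide 80% power to detect a 12-hour difference in duration of IV vasopressors" and, for the early phase, that "15 patients per group will provide 80% power to detect a 5 mcg/min decrease in norepinephrine equivalents at 24 hours". It allows for deaths: "anticipating a 25% mortality in patients with septic shock would need to enroll 149 patients to reach statistical significance". The power rests on 960 repository patients: "We then extracted their duration of vasopressors and the total norepinephrine equivalent doses at 24 hours".

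**The concern.** A skewed outcome justifies ranks. It does not justify leaving out a baseline measurement that may predict the outcome. A patient who enters on a high dose could be expected to be on more vasopressor at 24 hours and to need it for longer. In the early phase the candidate covariate is the pre-randomisation value of the outcome's own quantity. Since entry has a floor and no ceiling, the dose can vary between patients, and the randomisation does not balance it by design.

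If entry dose predicts outcome, the unadjusted test leaves explainable variation in the error term and gives up power that costs no patients. This is a matter of efficiency: the Mann-Whitney test keeps its type I error under randomisation, and the documents do not show the trial to be short of power. In the early phase the gain would apply to the pairwise 24-hour dose comparisons. It would not carry straight over to the choice of dose, which also weighs safety and favours the lower dose when effects are similar.

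**Working it through.** **The plan's own figures.** The 80% at 50 per group for 12 hours comes from bootstrapping internal records that are not in the documents, so it cannot be rerun. Two-sided alpha of 0.05 is assumed throughout, as sidedness is not stated.

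- By normal theory, the SD that gives 80% is 12 / [(1.960 + 0.842) × √(2/50)] = 21.4 h. With the published SD of 28.4 h, power is Φ[12 / (28.4 × 0.2) − 1.960] = Φ(0.153) = 56%. Neither figure settles the power under the repository distribution.
- Enrolment does reproduce: 50 / (1 − 0.25) = 66.7, so 67 per arm, and 2 × 67 + 15 = 149. The allocation agrees: 15 + 104/2 = 67.

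**Approximate gain from the stated 80%.** Adjustment multiplies residual variance by (1 − r²), so power is Φ[2.802 / √(1 − r²) − 1.960]:

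- r = 0.3: Φ(2.937 − 1.960) = 83.6%
- r = 0.5: Φ(3.235 − 1.960) = 89.9%

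**Simulation inputs.** r is not in the documents, so 0 to 0.5 is assumed.

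- Full trial: hours assumed log-normal with the published mean 54.9 and SD 28.4. The log-SD is √ln[1 + (28.4/54.9)²] = 0.487. Treated hours are multiplied by 1 − 12/54.9 = 0.781.
- Early phase: shift of 5 mcg/min. No SD is given; 4.72 and 4.53 are back-solved from the stated 80%.
- Tests: Mann-Whitney (tie- and continuity-corrected) against least squares on ranks with group and ranked baseline, no phase term. 10,000 trials per cell, 20,000 in the early phase.

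Hand check of the unadjusted full-trial figures, using relative efficiency 0.955: the shift is |ln 0.781| / 0.487 = 0.506 SD. At 50 per arm, Φ(0.506 × √25 × √0.955 − 1.960) is about 70%; at 67 per arm, with √33.5, about 82%.

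**Complete outcomes, power (%)**

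| Comparison | Mann-Whitney | Adjusted, r = 0 | 0.1 | 0.2 | 0.3 | 0.5 |
|---|---|---|---|---|---|---|
| Full trial, 50 per arm | 68.2-69.0 | 68.3 | 68.8 | 69.9 | 72.0 | 79.2 |
| Full trial, 67 per arm | 80.9-81.7 | 81.2 | 81.7 | 82.0 | 84.0 | 89.9 |
| Early phase, 15 per arm, SD 4.72 | 76.6-76.9 | 76.8 | 77.0 | 78.3 | 80.3 | 86.1 |
| Early phase, 15 per arm, SD 4.53 | 79.5-80.2 | 80.3 | 80.1 | 80.8 | 83.0 | 88.8 |

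**Full trial with 25% deaths, assumed independent of arm: power (%), Mann-Whitney then adjusted**

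| Death rule | Per arm | r = 0.3 | r = 0.5 |
|---|---|---|---|
| Ranked worst, unrelated to entry dose | 50 | 27.4-28.1, 28.8 | 27.4-28.1, 29.4 |
| | 67 | 34.6-35.9, 35.7 | 34.6-35.9, 38.4 |
| Ranked worst, related to entry dose as strongly as hours are | 50 | 27.7, 30.5 | 27.9, 36.4 |
| | 67 | 35.2, 38.5 | 36.4, 46.9 |
| Excluded, unrelated to entry dose | 50 | 54.4, 58.0 | 55.3, 67.0 |
| | 67 | 68.5, 72.1 | 67.9, 79.3 |
| Excluded, related to entry dose | 50 | 55.2, 58.3 | 57.2, 67.0 |
| | 67 | 68.4, 72.0 | 70.1, 79.8 |

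Where Mann-Whitney is shown as a range, it is the range over the values of r run. At r = 0 the change was −0.3 to +0.3 points in all cells run. Null rejection of the adjusted test was 4.5-5.4% (not run for exclusion with death related to entry dose). Differences of a point or less are within simulation noise.

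**The case against.** The strongest reply is that this is a preference. The planned test is valid, named in advance and justified, and the whole benefit turns on a correlation that the documents do not give. There are reasons for it to be low: weaning follows nursing judgment with no algorithm, and the 5 mcg/min entry floor narrows the dose range. At r of 0.2 or less the gain is barely above noise. All of that stands. It is why the point is optional and the gain is shown as a range.

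Second, the unstated handling of deaths matters far more. Ranking deaths worst takes unadjusted power at 50 per arm from about 69% to about 28% in this model, and adjustment does not repair that. This also stands; it is a separate gap in the plan.

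Third, the 24-hour dose cannot go below zero, and the early-phase model has no floor. A check with a floor at zero (15 per arm, SD 4.72, 6,000 runs) still gave a gain of about 3 points at r = 0.3 and 8-10 at r = 0.5. Unadjusted power fell to about 70% when roughly a quarter of placebo patients were at zero. So the absolute early-phase powers depend on the model, but the gains largely hold.

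Fourth, rank ANCOVA gives no effect in hours or mcg/min. That is fair, but the Mann-Whitney p-value gives none either.

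The regression sentence in item 5 does not already cover the point: it concerns secondary outcomes and names no covariate.

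**Conclusion.** The point holds as an optional improvement; the plan is not wrong here. With complete outcomes, adjustment is worth about 0-2 points of power at r of 0.2 or less, 3-4 at 0.3 and 8-11 at 0.5, with essentially no loss at r = 0.

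In the full trial with 25% deaths, the gain at r = 0.3 and r = 0.5 is:

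- about 0-1 and 2-3 points if deaths are ranked worst and unrelated to entry dose;
- about 3 and 9-11 if they are ranked worst and related to it;
- about 3-4 and 10-12 if they are excluded.

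These figures rest on assumed values of r, a log-normal outcome with the published mean and SD, a 12-hour effect applied as a proportional reduction, deaths independent of arm, and back-solved early-phase SDs. Confidence is medium, because the documents supply neither r nor the death rule.

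**What to change.** Before the 45-patient interim analysis:

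1. Pre-specify rank ANCOVA as the primary test for both comparisons, adjusted for norepinephrine-equivalent dose at the last reading before randomisation.
2. State the rule for converting other vasopressors to norepinephrine equivalents.
3. Keep the unadjusted Mann-Whitney test as a sensitivity analysis. A phase term is optional, because placebo and the continuing dose are allocated 1:1 in both phases.
4. State in the same text how deaths enter vasopressor hours, since the gain depends on it.
5. If entry dose can be extracted for the 960 repository patients, estimate r there first. Restrict that set to patients at or above the 5 mcg/min entry floor, which is not among the criteria listed for it; a wider dose range would probably overstate r.

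The cost is SAP wording, one time-stamped dose reading per patient and a written conversion rule. Eligibility needs only the threshold, so the last reading is a separate data item, but it should be in the medical record. Norepinephrine equivalents were already computed for the repository patients, so a conversion is in use and only needs stating. No extra patients are needed.

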7. GCS
8. APACHE IV scores
9. Blood gas data
10. Mortality data (30- and 90-day)
11. Culture data

12. Diagnosis data pulled from provider notes
13. MAR data including concomitant corticosteroid use and antibiotics
14. Imaging data, including CXRs and CTs
15. Vital sign data including temperature, heart rates, blood pressures for the duration of the admission

The standard current ICU level care will be provided to both study groups. Invasive blood pressure measurement, laboratory studies, and imaging studies will be done according to standard practices in septic shock for all groups in the trial.

Intravenous vasopressor will be weaned in both groups as tolerated for MAP goal of > 65 mmHg by the bedside nursing staff according to usual practice (no protocolized algorithm for vasopressor weaning exists, vasopressors are weaned, as long as targeted MAPs are maintained, according to nursing judgment).

Subjects admitted to the ICU with a diagnosis of sepsis and in shock as defined, for study purposes, as requiring any IV vasopressor of at least 5 mcg/min norepinephrine infusion (or equivalent) for at least 3 hours AND with adequate enteral access (oral, orogastric, nasogastric or pre-existing PEG) will be randomized to either midodrine 10 or 20 mg every 8 hours for 72 hours or placebo, to investigate the efficacy of midodrine in decreasing time to IV vasopressor liberation in patients with septic shock. Data collection will continue until hospital discharge.

A dose of up to 20 mg TID is chosen as it was the modal dose in a recent prospective study and is the upper end of dosing with predictable hemodynamic response in another study. The retrospective studies previously referenced reported varying doses up to 40 mg TID.

The standard current ICU level care will be provided to both study groups. Invasive blood pressure measurement, laboratory studies, and imaging studies will be done according to standard practices in septic shock for both arms of trial. Intravenous vasopressor will be weaned in both groups as tolerated for MAP goal of > 65 mmHg by the bedside nursing staff.

2. If this protocol involves study treatment, explain how a subject will be transitioned from study treatment when they have completed their participation in the study.

Subjects will receive the study drug or placebo for a pre-specified duration of 72 hours. We acknowledge that discontinuation of the study drug may result in the need to resume IV vasopressor therapy, however reinitiation of IV vasopressor therapy will be one of the secondary outcomes under study. Re-initiation of IV vasopressor therapy cannot strictly be considered a risk of study treatment as the rate of re-initiation of IV vasopressors in the reference group is not technically known and care providers (not study investigators) may opt to start midodrine in an unblinded manner rather than re-initiating IV vasopressor therapy.

Subject Compliance with Study Procedures

1. Explain how the study team will monitor the subject for compliance with the study procedures.

(e.g. study team will administer study drug/ study interventions, study drug inventory of dispensed and returned drug, diary etc.)

The study team, nursing staff and/or the investigational pharmacy (IDS) will keep a log.

2. Describe criteria for when a subject is considered to be non-compliant with study procedures.

(e.g. subject returns more than 20% of the study drug, subject misses 20% of study visits)

Non-compliance will be considered inability to administer more than 20% of the scheduled drug or placebo.

Bibliography

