Patients admitted to the ICU with a diagnosis of sepsis and in shock as defined, for study purposes, as requiring any IV vasopressor of at least 5 mcg/min norepinephrine infusion (or equivalent) for at least 3 hours AND with adequate enteral access (oral, orogastric, nasogastric or pre-existing PEG, will be screened by research nurse, study coordinator or study investigator by review of medical record in EPIC only. If subject meets study criteria then the research nurse, study coordinator or investigators will approach patient or surrogate for consent to participate in the study. For patients unable to provide consent due to illness, surrogate consent will be sought.

Following consent, women of childbearing potential will have a urine pregnancy test. Pregnant women will be excluded.

Study Treatment:

In the “early phase” the first 45 subjects will be randomized to one of 3 study arms (placebo, midodrine 10 mg or midodrine 20 mg thrice daily for 72 hours). The remaining 104 subjects will subsequently be randomized to one of 2 study arms, placebo or the more efficacious of the 2 midodrine doses (10 mg TID or 20 mg TID) as determined by the planned interim analysis.

Data collection from the subject’s medical record will continue until hospital discharge. Data to be collected will include the following:

1. Vasopressor(s) used by type
2. Vasopressors dose and duration
3. ICU and hospital length of stay
4. Basic lab values including CBC, makers of renal function, cardiac biomarkers (troponin, BNP)
5. Presence of central venous catheter, site and number
6. CVC dwell time

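### Mortality is analysed at 28 days but collected at 30 and 90 days, while data collection ends at hospital discharge, so 28-day status is not assured for patients discharged earlier

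*Combined protocol and SAP*

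**What the plan says.** All the relevant text is in the combined protocol and SAP.

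- **Outcome.** Statistical Considerations item 5 (secondary variable analysis) lists six outcomes. The fourth is "28-day mortality" and the fifth is "ICU mortality".
- **Test.** The same item says "We will employ the Chi square test for binary outcomes". It gives no rule for patients whose status is unknown.
- **End of collection, first statement.** Study Procedures item 1, under Study Treatment: "Data collection from the subject’s medical record will continue until hospital discharge". This sentence introduces the list of data to be collected.
- **Mortality data collected.** Item 10 of that list is "Mortality data (30- and 90-day". The list has no 28-day item and does not mention date of death.
- **End of collection, second statement.** Later in Study Procedures item 1, without reference to the medical record: "Data collection will continue until hospital discharge".

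No section describes contact after discharge, a registry search, or any other source of vital status once a patient has left hospital.

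**The concern.** Two things do not fit together. The time point to be analysed is not among the time points to be collected. And the rule on when collection stops, stated twice, falls before day 28, 30 or 90 for anyone discharged earlier.

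A chi-square test needs a yes or no for each patient. If staff stop at discharge, the analyst must either count discharged patients as alive, which turns the outcome into in-hospital death by day 28, or drop them, which removes survivors from the denominator. The plan does not choose between these.

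The stopping point is also not neutral between arms. The Background section expects shorter ICU and hospital stays as indirect effects of treatment, and hospital length of stay is itself a secondary outcome. Under the discharge cut-off, the arm that goes home sooner is watched for fewer days. If that is midodrine and discharged patients are counted as alive, the under-count leans in its favour.

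**Working it through.** The documents give no power, sample size or expected rate for 28-day mortality, so there is no stated figure to reproduce. The check sets out what each reading of the plan yields, then bounds the size.

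**Patients in the final comparison.** Enrolment is 149, of whom 15 are in the dose arm dropped after the early phase: 149 − 15 = 134. The allocation scheme agrees: 15 early-phase patients plus 104/2 = 52 gives 67 per arm, or 134. The sample size text also gives 149: 100/(1 − 0.25) = 133.3, rounded up to 134, plus 15.

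**Reading A: item 10 is carried out past discharge.**
- Alive at day 30 implies alive at day 28.
- A death in hospital has a date in the record.
- With dates of death kept, 28-day mortality follows exactly.
- With 30-day status alone, only post-discharge deaths on days 29 and 30 could be misclassified. If 0% to 2% of patients fall there (assumption; no figure in the documents), that is 134 × 0 to 134 × 0.02, or 0 to 2.7 patients.

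**Reading B: collection stops at discharge.** Every patient discharged alive before day 28 has unknown 28-day status. The documents give no discharge timing. If 30%, 50% or 70% leave alive before day 28 (assumption), that is 134 × 0.30 = 40, 134 × 0.50 = 67 or 134 × 0.70 = 94 patients.

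**Missed deaths under reading B.** Three assumptions are needed:
1. The 25% in Statistical Considerations item 3 ("anticipating a 25% mortality in patients with septic shock") is in-hospital mortality. The plan attaches no time point to it.
2. Every survivor is discharged before day 28.
3. A fraction *r* of those discharged die by day 28.

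Deaths in hospital: 134 × 0.25 = 33.5. Survivors: 134 − 33.5 = 100.5. Missed deaths: 100.5 × *r*. Share of all 28-day deaths: missed / (33.5 + missed).

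| *r* (assumed) | Missed deaths | Share of 28-day deaths |
|---|---|---|
| 3% | 3.0 | 3.0/36.5 = 8% |
| 5% | 5.0 | 5.0/38.5 = 13% |
| 10% | 10.1 | 10.1/43.6 = 23% |

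For each *r* these are upper values. Patients still in hospital at day 28 are fully observed, and if 25% already means 28- or 30-day mortality, the post-discharge deaths lie inside the 33.5.

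**Difference between arms under reading B.** The only difference in stay that the documents quantify is nearly 2 days of ICU stay, from a retrospective cohort cited in the Background. Assume that hospital stay is also 2 days shorter on midodrine, that post-discharge deaths are spread evenly over 14 days, and that each arm has about 50 survivors. Extra missed deaths on midodrine are then 50 × *r* × 2/14:
- *r* = 3%: 0.2
- *r* = 5%: 0.4
- *r* = 10%: 0.7

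A 7-day window doubles these to 0.4, 0.7 and 1.4.

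**The case against.** A reader might infer that 28-day mortality cannot be measured under this plan. The documents do not support that. Item 10 asks for mortality to day 90, which for many survivors must lie beyond discharge, so the investigators evidently mean to learn vital status later. The first discharge sentence concerns the medical record and introduces the very list that holds item 10. It is at least as natural to read item 10 as a specific exception as to let the general cut-off override it. On that reading only the 28 versus 30 day mismatch is left, and it is close to harmless.

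This objection stands against the strong claim but does not remove the point. The second discharge sentence carries no such qualification, item 10 names no source or method, and nothing asks for a date of death. Staff who follow the twice-stated rule would have no reason to look for the data.

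A reader might also infer a material bias towards midodrine. The direction is plausible, but the illustration puts the extra missed deaths at about one or fewer, and the documents give no difference in hospital stay from which to do better.

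It is also fair to say that the documents do not present 28-day mortality as the main safety measure. It is fourth among the secondary outcomes, and ICU mortality, which can be seen before discharge, is listed beside it.

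**Conclusion.** The plan contradicts itself on mortality. The analysis list and the collection list use different time points, and the discharge cut-off conflicts with the 30- and 90-day item as well as with the 28-day outcome. As written, 28-day status is not assured for patients discharged alive before day 28; whether it is obtained depends on which statement staff follow.

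The size cannot be computed from the documents. An upper range of 3 to 10 missed deaths in 134 patients holds only if 25% is in-hospital mortality, all of about 100 survivors leave before day 28, and 3% to 10% of them then die by day 28. If item 10 is carried out with dates of death, none is missed.

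The primary outcome, hours of IV vasopressor therapy, is not affected. The point should still be corrected: a listed outcome has no assured source of data, and its observation window depends on discharge, which the trial itself expects treatment to bring forward.

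**What to change.** 1. Use one mortality time point in both the secondary outcome list and the data collection list.
2. Exempt vital status and date of death from the discharge cut-off, in both places where it is stated, for all randomised patients through the last mortality time point kept (day 90 if 90-day mortality is retained).
3. Name the source: a record search for patients already discharged, and a call only where consent allows.
4. Say how unknown vital status is handled in the analysis.

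The cost is a wording change, a possible addition to the consent, and a record check for patients already discharged: roughly 100 in the final comparison if 25% die in hospital. Arranging this during the trial is cheap; status not sought then may be harder to recover later.
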